6.1 Study Procedures

EMPOWER Curriculum: EMPOWER is an adapted SEL and wellness education initiative delivered to a community of refugee families that was developed through a pre-pilot in the New Haven Afghan refugee community in 2020. Unlike traditional school-based SEL curricula, EMPOWER partners with community organizations to provide translated and trauma-informed wellness education to family units. The program combines in-person (socially distant) and remote delivery of culturally-informed physical, emotional, and medical wellness tools adapted from evidenced-based behavioral medicine, refugee trauma and recovery, and community health research (Table 2). Over two weeks, enrollees participate in six in-person sessions (two hours each). They also complete four, one-hour, weekly Zoom sessions during and beyond the in-person curriculum. At-home Zoom technical support is provided as needed. Each family unit is guided through in-person and online components by a facilitator. The EMPOWER curriculum focuses on the core competency of self-awareness, a core element of emotional competence, from the Collaboration for Academic Social and Emotional Learning (CASEL) framework.²³ Facilitators include interns, health-providers, and community partners. We have published a detailed EMPOWER manual, which we will iteratively modify, through an online request portal.²⁴

Intervention: We will use implementation science methods and apply an Intervention Mapping framework to refine and assess the adoption, acceptability, and feasibility of EMPOWER.¹⁸ The program will include virtual and in-person SEL, COVID-19 safety, and physical activity instructions. Program administrators will also respond to and track disclosure of and/or identification of mental health, medical, or other needs.

Data Collection and Measures: We will conduct a mixed methods evaluation—using concurrent qualitative and quantitative data collection and merged analysis²⁵—to survey parents and their children (over Zoom) at early and late time-points of their involvement in the program. Interview guides and survey tools will be developed with community partners and will be based upon previously-studied measures used for war-affected families.²⁶ In addition to demographic covariates (age, gender, languages, years in the US), we will collect data and assess implementation outcomes as well as primary and secondary outcome measures (Table 1). Questions will be asked to parents about each child and to the children directly.

Implementation measures (Aim 1) will include assessment of adoption, acceptability, and feasibility through parent and stakeholder evaluations and through rates of attrition. Outcome measures (Aim 2) will include (a) COVID-19 knowledge, measured via an established COVID-19 knowledge assessment¹⁷ and (b) children's SEL competence, measured by the Trait Meta-Mood Scale.¹⁶ Secondary outcomes and covariates will include the validated measures outlined in Table 1 that may modify intervention effectiveness. While timeline and small sample size in this pilot will likely not allow detection of pre-post differences in quality of life or behavioral health concerns such as stress or depressive symptoms, we will examine patterns in secondary outcomes to form hypotheses in preparation for future, larger-scale trials.

Table 2. EMPOWER Curricular Components

Pre-EMPOWER Preparedness

At Home: Consent Form Signed, Materials Delivered
At Home: Zoom Support, Zoom Orientation with Parents
Identification of Outdoor Space, Safe and Walkable

In-Person Curriculum (6 times, over 2 weeks)

COVID-19 symptom and temperature check
Hand-washing, clean space, social distance
Arrival art activity and materials provided
Lesson: COVID-19 Safety (symptoms and prevention)
Lesson: Physical Activity (eg breathing, yoga)
Lesson: Healthy Habits (eg healthy eating)
Lesson: SEL, Emotional Vocabulary (eg emotion bingo)
Lesson: Art Activity (eg painting emotions)
Wrap-Up: Homework, Breathing, Hand-Washing

Zoom Curriculum (1 time weekly, over 4 weeks)

Arrival: Mindfulness Exercises (eg 20 Questions)
Lesson: COVID-19 Safety (symptoms and prevention)
Breakout Lesson: Physical Activity (eg yoga)
Breakout Lesson: Homework check-in
Breakout Lesson: SEL, Emotional Vocabulary Games
Wrap-Up: Homework, Next Meeting

Intervention and Evaluation Schedule

	Info Session (All)	Pre- Evaluation (All)	EMPOWER (for Intervention Group)	Evaluation (Intervention)	Evaluation (Control)	EMPOWER (for Control Group)
Zoom Information Session	X					
Zoom Informed Consent		X				
Demographic Collected		X				
Outcome Evaluation						
COVID-19 Knowledge		X		X	X	
Trait Meta Mood Scale		X		X	X	
Secondary Outcomes: Afghan Symptom Checklist, PedsQL, PSC		X		X	X	
Implementation Outcomes				X		
EMPOWER Curriculum			X			X

6.1.1 Data Collection

After confirming verbal informed consent, data will be collected over Zoom with interpreters who speak the respondents' preferred languages.

- **Translated Data Collection Instruments**: Standardized data collection tools, which will be interpreted according to World Health Organization Standards include:
 - Trait meta mood scale¹⁶
 - Afghan symptom checklist²⁰
 - Pediatric quality of life²⁷
 - Perceived stress scale¹⁹
 - COVID-19 questionnaire,¹⁷ previously administered (uploaded in supporting documents)
- **Implementation Outcomes**: A qualitative survey guide will be developed with stakeholders to discuss feasibility and acceptability with parents, based upon prior piloted survey tools (uploaded in supporting documents).
- **Mode of Data Collection**: All surveys and interviews will be conducted over Zoom. After verbal informed consent is read in the respondent's preferred language, with permission, responses will be audio-recorded. Interviews will be transcribed verbatim in real-time with post-interview proofreading and comparison to the audio recordings. It is expected that all interviews and surveys will be approximately one hour in duration.
- **Compensation**: A \$25 gift card will be distributed to respondents after each interview. All interviews were approximately one hour in duration.

6.2 Method of Assignment/Randomization (if applicable)

Not applicable. Intervention and control group designations will be based upon geographic location to easily access the outdoor location of the EMPOWER program.

6.3 Adverse Events Definition and Reporting

Adverse event means any untoward medical occurrence associated with the use of an intervention in humans, whether or not considered intervention-related.

An adverse event (AE) or suspected adverse reaction is considered "serious" if, in the view of either the investigator or sponsor, it results in any of the following outcomes: death, a life-threatening adverse event, inpatient hospitalization or prolongation of existing hospitalization, a persistent or significant incapacity or substantial disruption of the ability to conduct normal life functions, or a congenital anomaly/birth defect.

Any adverse event will be evaluated determined severity and need for reporting to IRB.

6.4 Reaction Management

A referral network and network of experts in pediatric health, pediatric mental health, and adult refugee health have been compiled. If any medical, mental health, educational, or behavioral health needs are disclosed, patient navigators and the research team will ensure proper referrals and follow-up are followed.

6.5 Withdrawal Procedures

Participants may withdraw at any time by letting staff know or stopping attendance, and if requested, no new data will be collected, but previously collected data will be kept to maintain the integrity of the study.

6.6 Locations/Facilities

Locations will be secure, safe outdoor spaces near participants' homes (including, for example, outdoor parks, or parking lots) identified by and with refugee serving organizations in Connecticut, USA. Additional curricula will occur over Zoom, as will all surveys and interviews. Additionally, the entire curriculum is fully convertible to Zoom if needed, and if weather and/or COVID necessitates remote learning, this can happen at any point in the protocol.

7 Statistical Design

7.1 Sample Size Considerations

Following COVID-19 protocols, we will limit in-person attendance to a maximum of ten children from a maximum of four family units over five sessions. Therefore, we anticipate about 50 children from 20 family units, with 25 children from 10 families as waitlist controls. This is well within recommended pilot sample size of 15-25 to detect small to medium effect sizes.²⁸

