7.2 Planned Analyses

In this mixed methods study, we will perform concurrent qualitative and quantitative data collection and subsequent merged analysis. We will analyze quantitative data in Stata,²⁹ with statistical support from a biostatistician. Qualitative responses will be transcribed and coded by members of the research teams using NVivo®. We will identify emerging themes using the constant comparative method. A repeated measures linear mixed model approach will be used for analysis. The primary analyses will compare changes in COVID-19 knowledge and of emotional competence before and after participation between the intervention and wait-list control groups. Similar analyses will be measured for secondary outcomes.

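### Section 7.2 names no level above the child, although children enter as families and are taught in about five groups; intervals are too narrow if changes correlate within either

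*Combined protocol and SAP*

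**What the plan says.** Section 7.1 derives the sample size from teaching capacity. In-person attendance is capped at "ten children from a maximum of four family units over five sessions", and from this "we anticipate about 50 children from 20 family units, with 25 children from 10 families as waitlist controls".

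On the model, Section 7.2 says "A repeated measures linear mixed model approach will be used for analysis", and the Analysis Plan in Section 4 says the same. The contrast is stated as follows: "The primary analyses will compare changes in COVID-19 knowledge and of emotional competence before and after participation between the intervention and wait-list control groups". Neither section names a random effect, a covariance structure, robust standard errors, an intraclass correlation or a degrees-of-freedom method.

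Other parts of the protocol bear on the structure of the data:
- Section 5.3 recruits by family unit.
- Section 6.1 has parents answer about each of their children, so siblings can share a respondent.
- Section 5.1 and the schedule in 6.1 have the wait-list arm assessed before it is taught.
- Section 8.4 keeps attendance records.
- Section 6.2 assigns arms without randomisation: "Intervention and control group designations will be based upon geographic location to easily access the outdoor location of the EMPOWER program".

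**The concern.** Siblings share a home and, for part of the data, a reporting parent. Children taught together share lessons and peers over six two-hour in-person sessions aimed directly at both primary efficacy outcomes. Correlated changes within family and within teaching group are therefore plausible. A model that links only the two assessments of the same child treats 75 children as 75 independent changes. If they are not independent, the standard error of the between-arm difference is too small, the interval too narrow, and a null effect is declared positive more often than the nominal rate. Section 4 intends the results to inform larger trials, so an overconfident interval would carry over into their planning.

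**Working it through.** **The plan's own figures.** Five groups × 10 children = 50, and five groups × 4 families = 20. Both match 7.1 exactly. Each enrollee attends six in-person sessions (6.1). If the sessions in 7.1 meant those meetings, six would give 60 children and 24 families, which does not match. The five sessions of 7.1 are best read as five teaching groups. Children per family: 50/20 = 25/10 = 2.5.

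**Assumptions (not in the documents).** The variance of a child's change is set to 1. Let f be the share due to family, g the share due to teaching group (taught arm only, since controls are untaught when compared), and e = 1 − f − g. The test is two-sided at 5%. I take f = 0.2 as the main case and g = 0, 0.05 and 0.10.

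**Formulas for the variance of the arm difference.**
- True: (g/5 + f/20 + e/50) + (f/10 + (1 − f)/25).
- Child-level analysis: 1/50 + 1/25 = 0.060, SE 0.2449.
- Family-level analysis, where group variance is absorbed as if it were family variance: ((g + f)/20 + e/50) + (f/10 + (1 − f)/25).
- Actual type I error ≈ 2[1 − Φ(1.96 × SE used / SE true)].

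**Results at f = 0.2.** The control arm contributes 0.020 + 0.032 = 0.052 throughout.

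| g | True variance | True SE | True SE / child-level SE | Child-level type I error | Family-level SE | True SE / family-level SE | Family-level type I error |
|---|---|---|---|---|---|---|---|
| 0 | 0.026 + 0.052 = 0.078 | 0.2793 | 1.14 | 8.6% | 0.2793 | 1.00 | 5.0% |
| 0.05 | 0.035 + 0.052 = 0.087 | 0.2950 | 1.20 | 10.4% | 0.2820 | 1.05 | 6.1% |
| 0.10 | 0.044 + 0.052 = 0.096 | 0.3098 | 1.27 | 12.1% | 0.2846 | 1.09 | 7.2% |

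**Check by simulation.** I ran 20,000 null trials per setting, with t-tests on change scores. At g = 0, 0.05 and 0.10, child-level error was 9.1%, 10.5% and 12.7%, and family-level error 5.0%, 5.7% and 7.0%. Further runs gave 8.6–8.9%, 10.7–11.0% and 12.1–12.7% for the child level.

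**Which level matters more.** At g = 0.05, family accounts for 8.6 − 5.0 = 3.6 of the 10.4 − 5.0 = 5.4 points of excess, about two thirds. At g = 0.10 it accounts for 3.6 of 7.1 points, about half.

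**Range.** With f from 0 to 0.30 and g from 0 to 0.10 in the taught arm, child-level error by the formula runs from 5.0% (both zero) to 13.8% (f = 0.30, g = 0.10). With g from 0.01 to 0.10, the family-level SE needs multiplying by 1.01 to 1.11.

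**The case against.** The strongest reply is that 7.2 is brief rather than wrong. It names no random effects at all, a biostatistician is to support the analysis, and a mixed model can carry further levels. That is true, and the fault is an unspecified model rather than a stated wrong one. But nothing in the documents commits the analyst to a family or group term, and repeated measures are the only structure mentioned.

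Several stronger readings are tempting and are not supported:
- **That the standard errors are too small as a matter of fact.** This depends on positive correlations, which the documents do not give. With both at zero there is no error.
- **That family is already handled and only the group level is missing.** No family term appears in the plan.
- **That each group shares one site and one facilitator.** Section 6.6 speaks of several outdoor spaces and allows conversion to Zoom. Section 6.1 assigns a facilitator to each family without mapping facilitators to groups. The limit of ten covers in-person attendance only. The point needs only that children are taught together.
- **That the error is larger because controls also cluster.** If controls fell into groups of 4, 4 and 2 families with the same group correlation, a family-level analysis at f = 0.2 would have about 8% and 11% error at g = 0.05 and 0.10. No section describes such groups, and controls are untaught when compared. Clustering by shared location is possible but is an added assumption.

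Two further objections stand in part. A group variance from five groups is poorly estimated: in the simulation a moment estimate was zero or negative in 56%, 40% and 29% of trials at g = 0, 0.05 and 0.10. This argues for a sensitivity analysis beside the model, not for ignoring the level. Also, this is a non-randomised pilot with no stated significance level, and confounding by location may matter more than calibration. That limits the importance of the point, but intervals will still be reported and used.

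**Conclusion.** The point holds in conditional form. Children are recruited as families and taught in about five groups, yet the plan names no level above the child. Under an assumed family correlation of 0.2, the correct standard error is 1.14 times the child-level one with no group effect, and 1.20 and 1.27 times it at group correlations of 0.05 and 0.10 in the taught arm. True type I error is then about 9%, 11% and 12% in place of 5%. Adding family alone brings it to about 6% and 7% at the two positive group correlations, so the group level is a modest remainder. All of these rest on assumed correlations and on clustering by teaching group in the intervention arm only. The change should be made, because it is cheap and the structure is known in advance, but it does not decide whether the study is interpretable.

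**What to change.** In 7.2, and in the matching text of Section 4, state the random effects: child and family in both arms, and teaching group in the intervention arm only (a partially nested model), with small-sample degrees of freedom such as Kenward-Roger.

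Say also that the family and group effects act on change. With one assessment before and one after, plain random intercepts cancel from the pre-post contrast and leave its standard error uncorrected. Either model each child's change with family and group effects, or add family-by-time and group-by-time effects to the repeated measures model.

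Record the teaching-group identifier alongside the attendance records in 8.4.

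Because five groups will often give a zero variance estimate, pre-specify a sensitivity analysis of group-mean changes. One form compares the five group means with the ten control-family means, allowing unequal variances. In the simulation above its type I error was 4.6–4.9%. Report it beside the main model; the conclusion need not rest on whichever interval is wider.

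The cost is a sentence or two in the plan, one identifier, somewhat wider intervals and an imprecise group variance. None of this removes the confounding from assigning arms by location, which the report should state separately.

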Implementing and Evaluating a Wellness and Social-Emotional Learning Program for Refugee Children During the COVID-19 Pandemic: EMPOWER

(Emotions Program Outside the Clinic and Wellness Education for Refugees)

Protocol Number

2000030455

ClinicalTrials.gov Identifier: NCT04931888

Protocol and Statistical Analysis Plan

February 20, 2022

Version #3

Synopsis

Purpose

Our overall goal is to pilot an adaptation of an established Social-Emotional Learning (SEL) Program with novel wellness and COVID-19 safety components that are trauma-informed and culturally-specific in a resettled refugee community.

Objectives

In this pilot, “EMPOWER” (Emotions Program Outside the clinic and Wellness Education for Refugees), we aim:

1. To assess implementation outcomes (adoption, acceptability, and feasibility) of EMPOWER with refugee children and families during the COVID-19 pandemic through longitudinal evaluations and measurements of feasibility, acceptability, and attrition.
2. To evaluate the impact of EMPOWER by assessing (a) children’s SEL competence and (b) children’s and family’s COVID-19 knowledge.

Study Population

The study population will include families who are connected with Elena’s Light, a trusted community non-profit organization that supports refugee families in the New Haven region.

Because the model of adaptation and delivery will be culturally specific for Afghan refugees (the majority of recent refugees in the New Haven area are from Afghanistan), eligible participants will include Afghan refugee children, 5-15 years old, who have completed ≥ 1 year of school in US. One parent/guardian will also be surveyed in the pre- and post-evaluation on Zoom.

Number of Participants

A total of approximately 75 children from 30 family units will be recruited to participate, along with at least one parent/guardian from each family. This will include 50 children from 20 family units in the intervention group and 25 children from 10 family units in the control group.

Study Design

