Implementation measures (Aim 1) will include assessment of adoption, acceptability, and feasibility through parent and stakeholder evaluations and through rates of attrition. Outcome measures (Aim 2) will include (a) COVID-19 knowledge, measured via an established COVID-19 knowledge assessment and (b) children's SEL competence, measured by the Trait Meta-Mood Scale. Secondary outcomes and covariates will include the validated measures that may modify intervention effectiveness. While timeline and small sample size in this pilot will likely not allow detection of pre-post differences in quality of life or behavioral health concerns such as stress or depressive symptoms, we will examine patterns in secondary outcomes to form hypotheses in preparation for future, larger-scale trials.

Analysis Plan:

In this mixed methods study, we will perform concurrent qualitative and quantitative data collection and subsequent merged analysis. We will analyze quantitative data in Stata, with statistical support from a biostatistician. Qualitative responses will be transcribed and coded by members of the research teams using Dedoose. We will identify emerging themes using the constant comparative method. A repeated measures linear mixed model approach will be used for analysis. The primary analyses will compare changes in COVID-19 knowledge and of emotional competence before and after participation between the intervention and wait-list control groups. Similar analyses will be measured for secondary outcomes.

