5.2 Number of Participants

We will recruit a total of 75 children from a total of approximately 30 family units.

After recruitment, we will assign participants to an intervention group (50 children from 20 family units) and a wait-list control group (25 children from 10 family units) and will stagger administration of the EMPOWER curriculum to the two groups.

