7.3 Data Relevance

The data collected will specifically answer the research question of: can an adaptation of an established Social-Emotional Learning (SEL) curriculum effectively improve Social-Emotional wellness for refugee children and their families? By evaluating emotional competence and exploring secondary outcomes related to mental and behavioral health, we will be able to understand the impact of EMPOWER on refugee children's health.

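### Section 7.1 claims the sample can detect small to medium effects, but the planned between-group comparison of change cannot detect a small effect and reaches a medium one only if the pre-post correlation is about 0.74 or higher

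*Combined protocol and SAP*

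**What the plan says.** Section 7.1 starts from in-person attendance limits (ten children and four families at a time, over five sessions) and concludes: "Therefore, we anticipate about 50 children from 20 family units, with 25 children from 10 families as waitlist controls". It then adds, citing reference 28: "This is well within recommended pilot sample size of 15-25 to detect small to medium effect sizes". This is the only sample-size justification in the document. Section 5.2 gives the same group sizes.

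Section 7.2 fixes the primary comparison: "The primary analyses will compare changes in COVID-19 knowledge and of emotional competence before and after participation between the intervention and wait-list control groups". The model is named only as a repeated measures linear mixed model. Neither baseline adjustment nor a family random effect is specified. Section 6.2 says the groups are not randomized: "Intervention and control group designations will be based upon geographic location to easily access the outdoor location of the EMPOWER program".

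Two other statements bear on how results will be read. Section 7.3 says "The data collected will specifically answer the research question of: can an adaptation of an established Social-Emotional Learning (SEL) curriculum effectively improve" social-emotional wellness. Section 4 (Data Collection and Measures), repeated in 6.1, says "While timeline and small sample size in this pilot will likely not allow detection of pre-post differences in quality of life" or in behavioral health concerns. Those are secondary outcomes; the caveat does not mention COVID-19 knowledge or the Trait Meta-Mood Scale, the two primary efficacy outcomes.

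**The concern.** The sentence in 7.1 is offered as support for this trial's own numbers, so a reader will take it that 50 versus 25 children can detect small to medium effects on the primary outcomes. None of the quantities behind such a statement is given. A between-group comparison of change with 25 children in the smaller arm is not an obvious match for small effects.

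No go/no-go rule depends on a p-value, so no decision is directly at risk. What is at risk is the reading of the result. If the primary comparison is non-significant, 7.1 and 7.3 together invite the conclusion that a small or medium benefit has been ruled out.

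**Working it through.** **The plan's own figures.** The capacity arithmetic reproduces: 10 × 5 = 50 children, 4 × 5 = 20 families, 50 + 25 = 75. It explains the intervention group only; 7.1 gives no derivation for the 25 controls. The detection statement cannot be reproduced because its inputs are absent.

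**Inputs from the document.** 50 vs 25 children in 20 vs 10 families (5.2, 7.1), so 2.5 children per family; one pre and one post evaluation (schedule in 6.1); primary contrast is the between-group difference in change (7.2).

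**Assumptions, none in the document.** Two-sided 0.05; 80% power; small = 0.2 and medium = 0.5, in SDs of the score at one time-point; complete follow-up. The pre-post correlation r and the ICC of change within families are varied. A stable family effect cancels in change, so this ICC may be small.

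**Formulas.**

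- SE of the difference in change, in SD units: √[(1/50 + 1/25) × DE × 2(1 − r)] = √[0.06 × DE × 2(1 − r)]
- DE = 1 + (2.5 − 1) × ICC = 1 + 1.5 × ICC
- Detectable difference = k × SE. From the noncentral t, k = 2.839 with 73 df (independent children) and 2.902 with 28 df (30 families − 2, used when ICC > 0).
- Solved for r: r = 1 − d² / (0.12 × DE × k²)

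**Worked case, ICC = 0.** At r = 0.5, SE = √0.06 = 0.245, and 2.839 × 0.245 = 0.695 SD. With 0.12 × 2.839² = 0.967, the correlation needed is 1 − 0.25/0.967 = 0.742 for 0.5 SD and 1 − 0.04/0.967 = 0.959 for 0.2 SD.

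| ICC of change | Detectable SD, r = 0.5 | r = 0.7 | r = 0.8 | r needed for 0.5 SD | r needed for 0.2 SD |
|---|---|---|---|---|---|
| 0 | 0.70 | 0.54 | 0.44 | 0.74 | 0.96 |
| 0.05 | 0.74 | 0.57 | 0.47 | 0.77 | 0.96 |
| 0.1 | 0.76 | 0.59 | 0.48 | 0.79 | 0.97 |
| 0.2 | 0.81 | 0.63 | 0.51 | 0.81 | 0.97 |
| 0.5 | 0.94 | 0.73 | 0.60 | 0.86 | 0.98 |

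**Power.**

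| Effect | ICC of change | r = 0.5 | r = 0.7 | r = 0.8 |
|---|---|---|---|---|
| 0.5 SD | 0 | 52% | 74% | 89% |
| 0.5 SD | 0.2 | 41% | 61% | 78% |
| 0.5 SD | 0.5 | 32% | 49% | 65% |
| 0.2 SD | 0 | 13% | 18% | 25% |

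A simulation with families of two or three children and a family-weighted test (28 df, 40,000 runs) kept type I error at 0.049 to 0.052. It gave 50%, 40% and 31% power for 0.5 SD at r = 0.5 and ICC 0, 0.2 and 0.5.

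**Other readings.**

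- Total children needed at 2:1, independent, for 0.2 SD and 0.5 SD: 885 and 144 at r = 0.5; 534 and 87 at r = 0.7; 357 and 60 at r = 0.8. The plan has 75.
- The cited 15-25 read per group (1:1, change scores, r = 0.5) detects 1.06 to 0.81 SD.
- If parents' own scores are analysed with one parent per family (20 vs 10): 1.12 SD at r = 0.5 and 0.87 at r = 0.7.
- With 20% of families lost (40 vs 20 children, ICC 0): 0.78 SD at r = 0.5 and 0.60 at r = 0.7.
- A baseline-adjusted analysis replaces 2(1 − r) by 1 − r². With ICC 0 it needs r of about 0.70 for 0.5 SD and still 0.96 for 0.2 SD.
- A one-sided 0.05 test on change needs 0.67 and 0.95.
- A single-group paired test of 50 children at 0.5 SD of change would have 93% power, but that is not the planned comparison.

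**The case against.** The strongest reply is that the sentence cites a published pilot-size rule and makes no power claim. In its grammar, the detection wording can attach to the cited recommendation. Reference 28 is not available here, so whether 15-25 means per arm, in total, or a pilot that sizes a later trial cannot be checked. That uncertainty stands, and the fix allows for it. It does not save the sentence as written, because the rule is invoked to justify these numbers and no reading tested makes a small effect detectable.

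Second, the plan is silent on baseline adjustment and does not exclude it. With adjustment and independent children, power for 0.5 SD is 64% at r = 0.5 and 80.5% at r = 0.7, against 52% and 74% on change scores. This also stands: for a medium effect the claim is unverified, not refuted, and r could be high enough. But 7.2 describes a comparison of changes. With one pre and one post score and complete data, an unconstrained group-by-time test is that comparison.

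Third, the outcomes are labelled preliminary efficacy and the study a pilot. That sets a modest tone but says nothing about detectability, and the explicit caveat covers secondary outcomes only. Finally, Table 1 lists both parents and children as respondents, and the plan does not say how the two reports enter the model. The figures here use one score per child and should be read as approximate.

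**Conclusion.** The concern holds. The detection clause in 7.1 is not supported for the planned primary comparison. The small end (0.2 SD) is out of reach at any ordinary correlation: it needs r of about 0.96 on change scores or with baseline adjustment, and about 0.95 with a one-sided test. The medium end (0.5 SD) depends on an unstated r of at least about 0.74 with independent children, rising to 0.86 at an ICC of change of 0.5, or about 0.70 if the model were baseline-adjusted with independent children. These figures rest on the assumed two-sided 0.05, 80% power, 0.2 and 0.5 SD conventions and complete follow-up. Independence and no dropout favour the plan. The consequence is limited to interpretation, but this is the only justification given for the sample size, so it should be corrected.

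**What to change.** In 7.1, delete the clause about detecting small to medium effects. If reference 28 is a planning rule for sizing a later trial, say that and no more. Suggested replacement:

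> The 50 intervention children (20 families) follow from in-person capacity. No power calculation was done. At two-sided 0.05, 80% power and complete follow-up, the detectable between-group difference in change for 50 vs 25 independent children is about 0.70 SD at an assumed pre-post correlation of 0.5, 0.54 SD at 0.7 and 0.44 SD at 0.8. If changes correlate within families (ICC of change 0.2 to 0.5), it is about 0.81 to 0.94, 0.63 to 0.73 and 0.51 to 0.60 SD. The 95% CI half-width is about 0.49 SD at correlation 0.5 with independent children, and wider with clustering or dropout. If parents' own scores are analysed with one parent per family (20 vs 10), the detectable difference is about 1.1 SD at correlation 0.5. Estimates will be reported with 95% CIs, and non-significance will not be read as absence of a small or medium effect.

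Add the reason for 25 controls. Label any baseline-adjusted figure as such. Extend the small-sample caveat in Section 4 and Section 6.1 to the two primary efficacy outcomes.

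The cost is wording in these three places and a less favourable stated sensitivity. No extra participants are needed.
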